- If positive HBcAb with negative HBsAg and negative HBsAb, reflex testing for plasma HBV DNA (if positive, reflex HBeAg). If HBeAg is performed and found to be negative, reflex HBeAb.

— Hepatitis C virus (HCVAb) serology. Subjects who are HCVAb positive will have a HCV RNA test performed.

— HIV-1 genotype testing (protease and reverse transcriptase). The HIV-1 PR/RT genotype testing may not be performed for subjects that fail to meet other screening criteria.

- Review of adverse events and concomitant medications

Subjects meeting all of the inclusion criteria and none of the exclusion criteria will return to the clinic within 30-days after screening for the Day 1 Visit.

From the time of obtaining informed consent through the first administration of investigational medicinal product, record all serious adverse events (SAEs), as well as any adverse events related to protocol-mandated procedures on the adverse events case report form (eCRF). All other untoward medical occurrences observed during the screening period, including exacerbation or changes in medical history are to be captured on the medical history eCRF. See Section 7 Adverse Events and Toxicity Management for additional details.

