 - Subjects who meet the definition of HBV infection at Screening Visit (positive serum HBsAg or Positive HBcAb with quantifiable HBV DNA), will have plasma HBV DNA tested.

█ [REDACTED]

█ [REDACTED]

█ [REDACTED]

█ [REDACTED]

█ [REDACTED]

- Provide subject dosing diary to all subjects
- Dispense study drug

- Observed first dose administration of the assigned study drugs as described in Section 5.3
- Subjects should be instructed to take study drugs without regard to food. The subject should be counseled regarding the importance of adherence and taking their study medications at approximately the same time each day as directed by the Investigator.

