 - Metabolic assessments: Fasting (no food or drinks, except water, at least 8 hours prior to blood collection) glucose and lipid panel (total cholesterol, HDL, direct LDL, and triglycerides). If the subject has not fasted prior to the visit, the visit may proceed, but the subject must return within 72 hours in a fasted state to draw blood for the metabolic assessments. **(Weeks 12, 24, 48, 72, 96, 120, and 144)**
 - Estimated glomerular filtration rate according to the Cockcroft-Gault formula
 - Hematology profile: complete blood count (CBC) with differential and platelet count
 - Plasma HIV-1 RNA
 - CD4+ cell count
 - Plasma storage sample for safety, virology, or PK testing
 - For subjects who meet the definition of HBV infection at any visit
 - The following will be conducted by the central laboratory: HBsAb, HBsAg (qualitative and quantitative) and HBeAg (if negative, reflex HBeAb) **(Weeks 12, 24, 48, 72, 96 and every 24 weeks post Week 96)**
 - Plasma HBV DNA

- For subjects who do NOT meet the definition of HBV infection at any visit
 - The following will be conducted by the central laboratory: Hepatitis B surface antibody (HBsAb), Hepatitis B virus core antibody (HBcAb), and Hepatitis B virus surface antigen serology (HBsAg). Subjects who are HBsAg and/or HBcAb positive will have a reflex test for HBV DNA (viral load) (**Weeks 48, 96 and 144**)
- Hepatitis C virus (HCVAb) serology. Subjects who are HCVAb positive will have a HCV RNA test performed (**Weeks 48, 96 and 144**)
- Pharmacokinetic Blood Collection for subjects who are on study drug. Details of pharmacokinetic blood sampling procedures and sample management will be documented in the Pharmacokinetic Sample Collection, Processing, Storage, and Shipment Manual.
 - **Single Anytime, Trough and Post Dose PK Samples for all subjects on study drug:**
 - Subjects will have a single anytime pre or post-dose PK blood at **Weeks 8, 24 and 36**.

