Study Days are calculated relative to Study Day 1 for either the randomized phase analysis or the all B/F/TAF analysis, as appropriate. For events that occurred on or after the Study Day 1 date of either analysis, study days are calculated as (visit date minus the date of Study Day 1 plus 1). For events that occurred prior to Study Day 1 for either analysis, study days are calculated as (visit date minus the date of Study Day 1).

Last Study Date is the latest of the study drug (including B/F/TAF and DTG/F/TAF in both phases) start dates and end dates, the clinic visit dates, and the laboratory visit dates, including the 30-day follow-up visit date.

Baseline Value is defined as the last nonmissing value obtained on or prior to Study Day 1 for either the randomized phase analysis or the all B/F/TAF analysis, as appropriate. Subjects who actually received DTG+F/TAF in the randomized phase and received at least 1 dose of B/F/TAF in extension phase will have a new baseline value for the All B/F/TAF analysis.

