9.1. Analyses for HIV/HBV Coinfected Subjects

For all B/F/TAF analyses, subjects with HIV/HBV coinfection at baseline (ie. at the first dose of B/F/TAF) are defined as subjects who meet any of the following two criteria:

- Positive HBsAg on or prior to the first dose date of B/F/TAF (including both phases), or
- Negative HBsAg, negative HBsAb, positive HBcAb, and quantifiable HBV DNA (ie, HBV DNA \geq 20 IU/mL) on or prior to the first dose date of B/F/TAF (including both phases).

The following listings will be provided for subjects with HIV/HBV coinfection at baseline:

- Listing of adverse events
- Listing of liver-related laboratory tests and HBV DNA results

Subjects with incident HIV/HBV coinfection while on study drug (if any) are defined as subjects who are not HIV/HBV coinfecting at baseline for all B/F/TAF analyses and meet any of the following criteria:

- Positive HBsAg after the first dose date of B/F/TAF (including both phases) and on or prior to the date of permanent discontinuation of B/F/TAF (including both phases), or
- Negative HBsAg, negative HBsAb, positive HBcAb, and quantifiable HBV DNA (ie, HBV DNA \geq 20 IU/mL) after the first dose date of B/F/TAF (including both phases) and on or prior to the date of permanent discontinuation of B/F/TAF (including both phases), or
- Experience any of the following adverse events (ie, selected MedDRA PTs from the SMQ of “Liver Infections”) after the first dose date of B/F/TAF (including both phases) and on or prior to the date of permanent discontinuation of B/F/TAF (including both phases): Acute hepatitis B, Chronic hepatitis B, Congenital hepatitis B infection, Hepatitis B, Hepatitis B core antibody positive, Hepatitis B DNA assay positive, Hepatitis B surface antigen positive, Hepatitis B virus test positive.

The following listings will be provided for subjects with incident HIV/HBV coinfection while on B/F/TAF (if any):

- Listing of adverse events
- Listing of liver-related laboratory tests and HBV DNA results

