- For baseline coinfection, for all B/F/TAF analysis, the baseline would be adjusted based on the first dose of B/F/TAF (including both phases), when considering the different laboratory tests, take the latest, non-missing record on or prior to the first dose date of B/F/TAF (including both phases) for each test (eg, HBsAg, HBsAb, HBcAb, and HBV DNA).
 - The baseline coinfection status will be one of the three values: Yes/No/Null
 - The following tables provide combinations of HBV and HCV tests and the corresponding baseline coinfection status

HBsAg	HBsAb	HBcAb	HBV DNA	Coinfection Status	
Positive	-	-	-	Y	
Negative	Positive	-	-	N	
	Negative	Positive	Quantifiable	Y	
			Not Quantifiable	N	
			Missing	Null	
		Negative	-	N	
		Missing	Missing	Quantifiable	Null
				Not Quantifiable	N
	Missing			Null	
	Missing	Positive	Quantifiable	Null	
			Not Quantifiable	N	
			Missing	Null	
		Negative	-	N	
		Missing	Missing	Quantifiable	Null
				Not Quantifiable	N
Missing	Null				
Missing	Positive	-	-	Null	
	Negative	Positive	Quantifiable	Y	
			Not Quantifiable	Null	
		Missing	Null		
		Negative	-	Null	
	Missing	-	Null		
	Missing	-	-	Null	

HCVAb	HCV RNA	Coinfection Status
Positive	Quantifiable	Y
	Not Quantifiable	N
	Missing	Null
Negative	-	N
Missing	Quantifiable	Null
	Not Quantifiable	N
	Missing	Null

“-” means any value can be present, as it does not affect the classification

- For incident coinfection, all laboratory tests must share the same accession number and if any set of values meets the criteria, then the subject is considered to have incident coinfection
 - The incident coinfection status will be one of two values: Yes/Null
 - The following tables provide combinations of HBV and HCV tests that are considered “Y” for incident coinfection status (all others are considered Null)

HBsAg	HBsAb	HBcAb	HBV DNA	Coinfection Status
Positive	-	-	-	Y
Negative	Negative	Positive	Quantifiable	Y
Missing	Negative	Positive	Quantifiable	Y

HCVAb	HCV RNA	Coinfection Status
Positive*	-	Y
-	Quantifiable	Y

* Subjects with positive HCVAb postbaseline must also have negative or missing HCVAb at baseline in order to be considered as having incident HIV/HCV coinfection.

“-” means any value can be present, as it does not affect the classification

- For adverse events, the start date must be after the first dose date of B/F/TAF (including both phases) and on or prior to the last dose date

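### SAP 9.1 requires a negative HBsAb for coinfection by HBcAb and HBV DNA, the protocol does not, so some subjects followed on study as HBV-infected drop out of the HBV listings

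*SAP*

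**What the plan says.** **Protocol definition.** Section 6.2.2 (Day 1 Assessments) gives HBV infection as "positive serum HBsAg or Positive HBcAb with quantifiable HBV DNA". HBsAb plays no part.

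**Protocol testing.** At screening (Section 6.2.1), HBV DNA is reflexed if HBsAg is positive. For HBsAg-negative subjects the rule is "If positive HBcAb with negative HBsAg and negative HBsAb, reflex testing for plasma HBV DNA". At Weeks 48, 96 and 144 (Section 6.4), the rule for those not already classed as infected is wider: "Subjects who are HBsAg and/or HBcAb positive will have a reflex test for HBV DNA (viral load". The same rule applies every 48 weeks after Week 144 (Section 6.5.1) and at Weeks 48 and 96 of the open-label phase (Section 6.5.3). A separate schedule of HBV serology and HBV DNA applies "For subjects who meet the definition of HBV infection at any visit".

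**SAP definition.** SAP 9.1 accepts a positive HBsAg or, as the second laboratory route, "Negative HBsAg, negative HBsAb, positive HBcAb, and quantifiable HBV DNA", with quantifiable meaning at least 20 IU/mL. The same two routes serve baseline and incident coinfection. Incident status has a third route, a reported adverse event from a list of hepatitis B preferred terms.

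**SAP programming.** In Appendix 6 item 19, the baseline table sets HBsAg negative with HBsAb positive to N whatever the HBcAb or DNA result. The incident table counts positive HBsAg, or negative HBsAb with positive HBcAb and quantifiable DNA, and "all others are considered Null". For baseline status the programmer is told to "take the latest, non-missing record on or prior to the first dose date of B/F/TAF" for each test. SAP 3.8.1 says that subjects who switch from DTG + F/TAF "will have a new baseline value for the All B/F/TAF analysis".

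**The concern.** The protocol decides who is monitored for HBV, and the SAP decides who is reported as having it. If the SAP's rule is narrower, a subject in whom the trial's own testing found HBV DNA can be monitored as infected and still be missing from the tables and listings meant to show such subjects.

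The protocol gives ALT flare and post-treatment exacerbation of hepatitis B their own section (7.5.4). The SAP's HBV-specific safety output consists of the SAP 9.1 listings of adverse events, liver-related tests and HBV DNA, and SAP 5.2 tabulates coinfection status. The SAP gives no reason for the extra HBsAb condition. It also does not treat hepatitis C this way: under SAP 9.2, quantifiable HCV RNA after first dose is enough for incident coinfection whatever the antibody result.

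**Working it through.** No sample size or error rate is involved. The check is whether the two definitions disagree, and whether the disagreement can occur under the protocol's testing schedule.

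**1. Complete results.** HBsAg, HBsAb, HBcAb (each positive or negative) and HBV DNA (quantifiable or not) give 2 × 2 × 2 × 2 = 16 patterns.

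- Protocol, infected: 8 patterns with positive HBsAg, plus 2 with negative HBsAg, positive HBcAb and quantifiable DNA (HBsAb negative or positive) = 10.
- SAP, coded Y: the same 8, plus the HBsAb-negative one of those 2 = 9.
- Difference: 10 − 9 = 1. The pattern is HBsAg negative, HBsAb positive, HBcAb positive, DNA quantifiable. The SAP codes it N at baseline and Null for incident status.

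**2. Missing results allowed.** There are now 3 × 3 × 3 × 3 = 81 patterns.

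- Protocol: 27 with positive HBsAg, plus 2 (HBsAg negative or missing) × 3 (any HBsAb) with positive HBcAb and quantifiable DNA = 27 + 6 = 33.
- SAP: 27, plus 2 with negative HBsAb = 29.
- Difference: 33 − 29 = 4. These are the pattern above and three with HBsAg or HBsAb missing. Those three are Null at baseline and for incident status.

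**3. When the discordant complete pattern can be seen.**

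| Time | HBV DNA reflexed in an HBsAg-negative, HBcAb-positive subject? | HBsAb-positive subject tested? |
|---|---|---|
| Screening (Protocol 6.2.1) | Only if HBsAb negative | No |
| Day 1 (6.2.2) | Only if the definition was met at screening | No |
| Weeks 48, 96, 144 (6.4) | Yes | Yes |
| Every 48 weeks after Week 144 (6.5.1) | Yes | Yes |
| Weeks 48 and 96 OL (6.5.3) | Yes | Yes |

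The definitions therefore coincide on screening and Day 1 data. They can diverge from Week 48 on.

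**4. Where the divergence lands in the SAP.**

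- *Subjects randomized to B/F/TAF.* Baseline status uses results up to the first randomized dose, so it is unaffected. Incident status is affected.
- *DTG-to-B/F/TAF group.* The baseline is reset at the first open-label dose, so blinded-phase results from Week 48 on feed into it. A subject whose latest pre-switch results show the discordant pattern is coded N. A subject in whom the pattern appears only in the open-label phase is Null for incident status.

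**5. Can the adverse event route recover them?** Only in part. It needs a listed term with onset after the first B/F/TAF dose. Protocol 7.1.3 says laboratory abnormalities without clinical significance are not recorded as adverse events, so low-level DNA need not produce one. The route also cannot change a switcher's baseline status.

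**The case against.** The strongest reply is that the SAP did not invent the HBsAb condition. Protocol 6.2.2 states its definition in terms of the screening visit, and the screening reflex rule already requires negative HBsAb before DNA is measured in an HBsAg-negative subject. SAP 9.1 can be read as spelling that algorithm out. This stands for screening data. It does not carry over to Week 48 and later, where the protocol drops the HBsAb filter and still refers to subjects who meet the definition at any visit.

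A second reply is that Protocol Section 8.6 specifies no HBV analysis, so a SAP may choose its own analysis definition, and its no-change statement (SAP 7.7) is not literally contradicted. That also stands. But a definition narrower than the one used to follow subjects should be stated as such and justified, and it is not.

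Stronger readings that the documents do not support:

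- *Baseline coinfection is misclassified in both groups.* Step 3 of the working rules this out for subjects randomized to B/F/TAF.
- *Hepatitis flares will be missed.* SAP 7.2.4 summarizes AST and ALT above 3, 5, 10 and 20 × ULN regardless of HBV status and lists subjects above 3 × ULN. All adverse events (SAP 7.1.6) and chemistry results (SAP 7.2) are listed too.
- *A head count can be estimated from antibody prevalence.* The documents give no HBcAb or HBsAb prevalence. Such a count would in any case be of antibody patterns, not of subjects with quantifiable DNA.
- *Using the latest record is a further error, because a switcher whose DNA became unquantifiable before the switch is coded N.* This follows from the SAP's stated choice to define baseline at the first B/F/TAF dose. Carrying an earlier Y forward would be a preference, not a correction.

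**Conclusion.** The mismatch is real but limited. Of the 16 complete result patterns, one is HBV-infected under the protocol and not under the SAP. It can arise only from testing at Week 48 or later. It affects incident status in both groups and the reset baseline status of the DTG-to-B/F/TAF group.

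Affected subjects would be absent from the SAP 9.1 listings unless a listed hepatitis B term is reported. Affected switchers would also be absent from the Yes category in SAP 5.2. Their data remain in the general adverse event, laboratory and liver-test outputs. No endpoint, comparison or efficacy result depends on this.

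The number of subjects is probably small, but the documents give nothing from which to calculate it. The conclusion assumes that HBV DNA is tested as the protocol schedules it. A DNA result obtained outside that schedule before first dose could also be affected.

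**What to change.** In SAP 9.1 and in both HBV tables of Appendix 6 item 19 (baseline and incident), define coinfection as positive HBsAg, or positive HBcAb with HBV DNA of at least 20 IU/mL, irrespective of HBsAb. The discordant complete pattern then becomes Y, as do the three patterns with a missing HBsAg or HBsAb. The latest-record rule and the reset baseline can stay as they are, so a switcher gains a Yes only if the latest HBV DNA before the first B/F/TAF dose is still quantifiable.

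If the sponsor prefers to keep the HBsAb restriction, SAP 9.1 should say that it is narrower than the protocol's definition and give the reason.

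The cost is a change of wording and edits to two look-up tables. The protocol already schedules every test needed. The downside is slightly longer listings.

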9.2. Analyses for HIV/HCV Coinfected Subjects

For all B/F/TAF analysis, subjects with HIV/HCV coinfection at baseline (ie, at the first dose of B/F/TAF) are defined as subjects with positive HCVAb and quantifiable HCV RNA (ie, HCV RNA \geq 15 IU/mL) on or prior to the first dose date of B/F/TAF (including both phases). The following analyses will be provided for subjects with HIV/HCV coinfection at baseline:

- Listing of adverse events
- Listing of liver-related laboratory tests and HCV RNA results

Subjects with incident HIV/HCV coinfection while on study drug for all B/F/TAF analysis are defined as subjects who are not HIV/HCV coinfecting at baseline for all B/F/TAF analysis and meet any of the following criteria:

- Positive HCVAb after the first dose date of B/F/TAF (including both phases) and on or prior to the date of permanent discontinuation of B/F/TAF (including both phases) with baseline HCVAb Negative or missing, or
- Quantifiable HCV RNA (ie, HCV RNA \geq 15 IU/mL) after the first dose date of B/F/TAF (including both phases) and on or prior to the date of permanent discontinuation of B/F/TAF (including both phases), or
- Experience any of the following adverse events (ie, selected MedDRA PTs from the SMQ of “Liver Infections”) after the first dose date of B/F/TAF (including both phases) and on or prior to the date of permanent discontinuation of B/F/TAF (including both phases): Acute hepatitis C, Chronic hepatitis C, Hepatitis C, Hepatitis C antibody positive, Hepatitis C RNA positive, Hepatitis C virus test positive.

The following listings will be provided for subjects with incident HIV/HCV coinfection while on B/F/TAF:

- Listing of adverse events
- Listing of liver-related laboratory tests and HCV RNA results

11. SOFTWARE

SAS® Version 9.4 (SAS Institute Inc., Cary, NC.) is to be used for all programming of tables, listings, and figures.

nQuery Advisor® Version 6.0 (Statistical Solutions, Cork, Ireland.) is to be used for sample size and power calculation.

12. SAP REVISION

Revision Date (dd month, yyyy)	Section	Summary of Revision	Reason for Revision

13. APPENDICES

- Appendix 1. Study Procedures Table
- Appendix 2. Cardiovascular or Cerebrovascular Events
- Appendix 3. Hepatic Events
- Appendix 4. Adverse Events of COVID-19
- Appendix 5. Determining Missing and Virtual Visits Due to COVID-19
- Appendix 6. Programming Specification

Appendix 1. Study Procedures Table

Appendix Table 1. Study Procedures Table (Blinded Phase)

Study Procedures	Screening ^a	Day 1 ^b	4	8	12	24	36	End of Week ^{e, q}								Post-Week 144 ^{e, r} Every 12 Weeks	End of Blinded Treatment Visit	30-Day Follow-up ^p	Early Study Drugs DC ^c
								48	60	72	84	96	108	120	132				
Informed Consent	X																		
Medical History	X																		
Concomitant Medications	X	X	X	X	X	X	X	X	X	X	X	X	X	X	X	X	X	X	X
Adverse Events	X	X	X	X	X	X	X	X	X	X	X	X	X	X	X	X	X	X	X ^f
Complete/Symptom- Directed Physical Exam	X	X	X ^d	X ^d	X ^d	X	X ^d	X	X ^d	X ^d	X ^d	X	X ^d	X ^d	X ^d	X	X ^d	X	X ^{d, f}
12-Lead ECG (performed supine)	X	X				X		X				X				X	X ^w	X	
Questionnaires		X	X		X			X											
Height	X																		
Vital signs (blood pressure, pulse, respiration rate, and temperature), including Weight	X	X	X	X	X	X	X	X	X	X	X	X	X	X	X	X	X	X	
Urinalysis	X	X	X	X	X	X	X	X	X	X	X	X	X	X	X	X	X	X	
Urine Pregnancy Test ^g		X	X	X	X	X	X	X	X	X	X	X	X	X	X	X	X	X	
Serum Pregnancy Test	X																		
Chemistry Profile ^h	X	X	X	X	X	X	X	X	X	X	X	X	X	X	X	X	X	X	
Metabolic Assessments ⁱ		X			X	X		X		X		X		X		X	X	X	
Estimated Glomerular Filtration Rate	X	X	X	X	X	X	X	X	X	X	X	X	X	X	X	X	X	X	
Hematology Profile ^j	X	X	X	X	X	X	X	X	X	X	X	X	X	X	X	X	X	X	
Plasma HIV-1 RNA	X	X	X	X	X	X	X	X	X	X	X	X	X	X	X	X	X	X	
CD4+ Cell Count	X	X	X	X	X	X	X	X	X	X	X	X	X	X	X	X	X	X	
CCI																			

Study Procedures	Screening ^a	Day 1 ^b	4	8	12	24	36	End of Week ^{c, q}								Post-Week 144 ^{c, r} Every 12 Weeks	End of Blinded Treatment Visit	30-Day Follow-up ^p	Early Study Drug s DC ^c
								48	60	72	84	96	108	120	132				
HCV Serology ^u	X							X				X			X	X			
HIV-1 Genotype ^k	X																		
HIV-1 Genotype/Phenotype ^e																		X ^e	
Single PK Sample ^l				X		X	X												
Trough and Post Dose PK Sample ^m			X		X														
CCI																			
Randomization ^v		X																	
Provide subject dosing diary to subjects		X	X	X	X	X													
CCI																			
CCI																			
HBV blood panel ^l	X				X ^t	X ^t		X ^t		X ^t		X ^t		X ^t		X ^t	X		
Plasma HBV DNA ^t		X	X	X	X	X	X	X	X	X	X	X	X	X	X	X	X	X	X
Study Drug Dispensation		X ^b	X	X	X	X	X	X	X	X	X	X	X	X	X	X	X	X ^s	
Study Drug Accountability			X	X	X	X	X	X	X	X	X	X	X	X	X	X	X	X	X

- a Evaluations to be completed within 30 days prior to Day 1.
- b Initiation of the first dose of study drug is to take place in-clinic following completion of study procedures at the Day 1 visit.
- c Early Study Drugs Discontinuation visit to occur within 72 hours of last dose of study drug. Subjects will be asked to continue attending the scheduled study visits through the End of Blinded Treatment Visit even if the subject discontinues study drug.
- d Symptom-directed physical examination as needed.
- e HIV-1 genotype and phenotype testing for subjects with virologic failure. Following virologic rebound, subjects will be asked to return to the clinic (2-3 weeks later) prior to the next scheduled visit or at the next scheduled study visit, for a HIV-1 RNA and HIV-1 genotype and phenotype (reverse transcriptase, protease and integrase genotype and phenotype) blood draw. Based on the results of this testing, subjects should be managed according to the Virologic Rebound Schema (Protocol Section 6.12).
- f Any adverse event or test showing abnormal results that is believed to have a possible or probable causal relationship with the study drug will be repeated weekly (or as often as deemed prudent by the Investigator) until the abnormality is resolved, returns to baseline, or is otherwise explained.
- g Females of childbearing potential only. Positive urine pregnancy tests will be confirmed with a serum test.

- h Chemistry profile: alkaline phosphatase, AST, ALT, GGT, total bilirubin, direct and indirect bilirubin, total protein, albumin, LDH, CPK, bicarbonate, BUN, calcium, chloride, creatinine, glucose, phosphorus, magnesium, potassium, sodium, uric acid and amylase (reflex lipase testing is performed in subjects with total amylase > 1.5 x ULN). At Day 1, Weeks 12, 24, 48, 72, 96, 120 and 144, every 24 weeks post Week 144, and End of Blinded Treatment Visit, analyses of glucose will be done as part of the fasting metabolic assessments every 24 weeks and not as part of the chemistry profile. Additionally: TSH will be analyzed at Screening, Day 1, Weeks 24, 48, 72, 96, 120, and 144 followed by every 24 weeks post Week 144, End of Blinded Treatment Visit and Early Study Drugs Discontinuation visit. PT/INR to be performed at Day 1.
- i Fasting (no food or drinks, except water, at least 8 hours prior to blood collection) glucose and lipid panel (total cholesterol, HDL, direct LDL, triglycerides). If the subject has not fasted prior to the visit, the visit may proceed, but the subject must return within 72 hours in a fasted state to draw blood for the metabolic assessments.
- j CBC with differential and platelet count.
- k The Investigator must have received the results from the screening genotype report before proceeding with the Day 1 visit. Screening genotype report must show sensitivity to TFV and FTC. If genotype results from a local laboratory obtained ≤ 90 days prior to screening visit date show sensitivity to these drugs, this genotype will be acceptable to fulfill this inclusion criterion in the event that the genotype obtained at screening is not yet available and all other inclusion/exclusion criteria have been confirmed.
- l A single PK blood sample will be collected at any time pre or post-dose
- m A trough PK blood sample will be collected between 20-28 hours following the last dose. Following an observed dose, a single post dose blood sample will be collected between 1 and 4 hours post dose.
- n [REDACTED]
- o [REDACTED]
- p Only required for those subjects not enrolling in the open-label rollover extension, those subjects who prematurely discontinue study drugs and do not continue in the study through at least one subsequent visit after the Early Study Drugs Discontinuation Visit. For the purpose of scheduling a 30-Day Follow-Up Visit, a ± 6 days window may be used.
- q Study visits are to be completed within ± 2 days of the protocol-specified visit date based on the Day 1 visit through Week 12 and completed within ± 6 days through to Week 144, unless otherwise specified. The visit window at Weeks 48, 96, and 144 will be ± 6 weeks of the protocol-specified visit date.
- r After Week 144, all subjects will continue to take their blinded study drug and attend visits every 12 weeks until the End of Blinded Treatment Visit. Visit window of ± 6 days for study visits post Week 144.
- s Open-label study drug, B/F/TAF FDC will be dispensed to subjects participating in the Open-Label Rollover extension for up to 48 weeks.
- t HBV blood panel will be performed at Screening (Hepatitis B virus surface antigen (HBsAg), Hepatitis B virus surface antibody (HBsAb) and Hepatitis B virus core antibody (HBcAb)). For subjects who meet the definition of HBV infection at any visit: The following will be conducted by the central laboratory: HBsAb, HBsAg (qualitative and quantitative) and HBeAg (if negative, reflex HBeAb) (Weeks 12, 24, 48, 72, 96 and every 24 weeks post Week 96) and Plasma HBV DNA (every visit). For subjects who do NOT meet the definition of HBV infection at any visit: The following will be conducted by the central laboratory: Hepatitis B surface antibody (HBsAb), Hepatitis B virus core antibody (HBcAb), and Hepatitis B virus surface antigen serology (HBsAg). Subjects who are HBsAg and/or HBcAb positive will have a reflex test for HBV DNA (viral load) (Week 48, 96 and 144 and every 48 weeks post Week 144)
- u Hepatitis C virus (HCVAb) serology. Subjects who are HCVAb positive will have a HCV RNA test performed (Week 48, 96 and 144 and every 48 weeks post Week 144)
- v Randomization may be performed up to 3 days prior to the in-clinic Day 1 visit provided that all screening procedures have been completed and subject eligibility has been confirmed.
- w To be performed every 48 weeks.

